#### 4.1.5 Randomization

## 4.1.5.1 Confirmation of Eligibility

To be eligible for randomization, subjects must satisfy all inclusion/exclusion criteria, including the following inclusion criteria that are expected to be confirmed during the 4-week Baseline Symptom Assessment: Inclusion Criterion #7: evidence of EoE as defined by  $\geq 15$  PEAK eosinophils/HPF; Inclusion Criterion #8: in the daily diary, report episodes of dysphagia  $\geq 3$  days per 7 days during the last 14 days of the 4-week Baseline Symptom Assessment; Inclusion Criterion #9: completion of the daily diary on at least 5 out of each 7 days during the last 14 days of the Baseline Symptom Assessment and Exclusion Criteria #24: a serum cortisol level <16  $\mu$ g/dL (440 nmol/L) at 60 minutes with adrenocorticotropic hormone (ACTH) stimulation test using 250  $\mu$ g cosyntropin administered intramuscularly (i.e., an abnormal result on the ACTH stimulation test). The ACTH stimulation test should have been completed before entry into the 4-week Baseline Symptom Assessment, however the results of the test may be pending.

If the Investigator confirms eligibility criteria are met, he or she will randomize the subject using the Interactive Web Response System (IWRS). The IWRS will confirm the eligibility of the subject pertaining to histology (i.e., confirm histological evidence of the EoE diagnosis as per Inclusion Criterion #7: evidence of EoE as defined by ≥15 PEAK eosinophils/HPF), and provide the randomization number to the Investigator and the Sponsor.

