#### 8.0 STATISTICS

## 8.1 Determination of Sample Size

Part 1 includes a sample size with 100 subjects, in which 20 patients are randomized each to 1.5 mg HS, 1.5 mg BID, 3 mg HS, 3 mg BID, and placebo in the ratio 1:1:1:1:1. See also the discussion of randomization in Section 4.1.5.2.

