Due to lack of previous data, estimating power for the secondary endpoint of reduction in number of dysphagia episodes is difficult. We expect that majority of control group will range between 25-35 dysphagia episodes per week at baseline. We expect a placebo effect corresponding to a 20-30% reduction, implying a reduction of 5-10 episodes. If we assume that the range of reduction for patients in control group is 0 to 15 episodes (and a normal distribution), this would correspond to a standard deviation of approximately 15/6=2.5 episodes. We also expect treatment group to also have 25-35 dysphagia episodes per week at baseline, and a reduction of 30-60% with treatment, implying a reduction of 7 to 21 episodes. If we assume that the range of reduction for patients in treatment group is 0 to 30 episodes (and a normal distribution), this would correspond to a standard deviation of approximately 30/6=5 episodes. Given the uncertainty of these estimates, our conservative approach assumes standard deviations of 4.5 and 7.5 for control and treatment group (respectively) for the reduction in number of dysphagia episodes. Given these assumptions, we have 80% power for 20 active dose patients vs. 20 control patients to detect a mean difference in reduction between groups of 5.0 episodes. This calculation is for a single active arm vs. control and does not factor in the multiplicity of having 4 potential doses to test. Assuming independence, a conservative Bonferonni approach would provide 80% power for a mean difference in reduction between groups of 6.3 episodes per arm, indicating the study is powered for an effect size of 5.0 to 6.3 episodes in reduction of dysphagia episodes for each of the doses.

The study has other important objectives which require sufficient sample size. The sample size of a total of 100 subjects as specified for the primary endpoint is considered sufficient to adequately evaluate the measurement properties of the new PRO instrument, and assess the amount of change that is clinically meaningful and to establish cut offs for Response and Relapse.

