6.6. STATISTICAL TESTS

The default significant level will be 5%; confidence intervals will be 90% and all tests will be one-sided.

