7.4. MULTIPLE COMPARISONS/ MULTIPLICITY

The primary analysis of the primary efficacy variable will be performed using a gatekeeping strategy to preserve Type I error. This strategy is described in section 16.1.3.

The analysis of the secondary efficacy parameter of number of dysphagia episodes will use a Holm-Step down procedure (Holm, 1979). This is described in section 16.2.3.4.

All other statistical testing performed is considered descriptive only and no adjustments will be performed for multiplicity.

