Copyright © 2009, 2010, 2012, 2016, 2018 IQVIA. All rights reserved. The contents of this document are confidential and proprietary to IQVIA Holdings Inc. and its subsidiaries. Unauthorized use, disclosure or reproduction is strictly proh bited.

Page 45 of 70

percentages.

No statistical testing will be performed.

16.2.3.4. Analysis of Change from baseline in each of Global EoE Symptom Score, Total EREFs Score, Number of Dysphagia Episodes, 7-day EEsAI total score, 7-day EEsAI VDQ and AMS subscores The change from baseline in each of Global EoE Symptom Score (see section 16.2.1.4), 7-day EEsAI total score (see section 16.2.1.6) and 7-day EEsAI VDQ and AMS subscores (see section 16.2.1.7) will be summarized as continuous variables, and analysis of covariance (ANCOVA) will be used to compare the mean change from baseline in each of the APT-1011 dosing groups to placebo, at the Week 12 visit, with the estimated mean difference, 90% confidence interval of the mean difference and 1-sided p-values provided. This statistical testing at Week 12 is considered descriptive only and no adjustments will be made for multiple comparisons. The ANCOVA models will include the factors described in section 7.1.

All these change from baseline analyses will only include data while subjects are receiving double-blind study drug. Data will not be not included for visits after a histologic non-responder at Week 12 had received single-blind (to subject) APT-1011 3 mg BID in Part 2.

For the analysis of change from baseline in the number of dysphagia episodes (see section 16.2.1.5) and dysphagia free days, for each dose that meets the criterion for statistical significance on the primary efficacy outcome, a Wilcoxon Rank-Sum test will be used to test whether the reduction in the number of dysphagia episodes from baseline is larger for the APT-1011 dosing group compared to the control.

Holm's step-down procedure (Holm, 1979) will be used to control the overall Type I error at 0.05, where the number of doses considered for inferential testing is equal to the number of doses that meet statistical significance for the primary efficacy analysis.

Holm's step down procedure will be implemented as follows:

Let the number of APT-1011 doses that meet statistical significance in the primary efficacy analysis be represented by d (where d is between 1 and 4 inclusive for this study).

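### The only Holm-controlled secondary test, on dysphagia episodes, ignores the baseline count and gives up some power, by an amount the documents do not fix

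*SAP*

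**What the plan says.** SAP 16.2.3.4 states that "a Wilcoxon Rank-Sum test will be used to test whether the reduction in the number of dysphagia episodes from baseline is larger" in the dosing group than in the control. The comparison is made for each dose that succeeds on histology, and "Holm's step-down procedure (Holm, 1979) will be used to control the overall Type I error at 0.05". SAP 7.4 leaves every other secondary comparison outside that control: "All other statistical testing performed is considered descriptive only and no adjustments will be performed for multiplicity". SAP 6.6 sets the convention that "confidence intervals will be 90% and all tests will be one-sided".

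The test is a plain two-sample comparison. The covariates in SAP 7.1 (stricture, steroid response, region, asthma/allergy, EREFs, PPI status) enter the ANCOVAs of the descriptive endpoints but not this test, and the list has no baseline dysphagia count. The Bayesian model for the same endpoint (SAP 16.1.5) has dose, frequency and the two strata only.

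Protocol 8.1.1 describes the expected effect in percentages and then converts it: "We expect a placebo effect corresponding to a 20-30% reduction, implying a reduction of 5-10 episodes" for placebo, and 30-60%, or 7 to 21 episodes, for active treatment. It takes 25-35 episodes per week as the baseline for most subjects.

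**The concern.** If benefit is proportional to the starting count, a subject with more episodes shows a larger raw drop for the same percentage benefit. Ranking raw drops then partly ranks baseline burden. That adds noise which the diary could remove, because the baseline 14-day count is already collected.

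At stake is the chance of detecting a dysphagia benefit on the only secondary endpoint that carries formal inference. There are about 20 subjects per arm, and the first Holm step is 0.05/4 = 0.0125 if all four doses pass the primary test.

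**Working it through.** **1. The protocol's own power.** Protocol 8.1.1 assumes SDs of 4.5 (control) and 7.5 (active), with 20 per arm.

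- Pooled SD = √((4.5² + 7.5²)/2) = √38.25 = 6.185. Standard error of the difference = 6.185 × √(2/20) = 1.956.
- At 5.0 episodes, one-sided 0.05: 5.0/1.956 − 1.645 = 0.911, so power is 81.9% (80.7% with the t distribution).
- At 6.3 episodes, one-sided 0.0125: 83.6% by the normal formula and 80.2% by Welch.

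Both stated 80% figures therefore reproduce.

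**2. Is the expected effect proportional?** The episode ranges are baseline times percentage: 25 × 20% = 5 and 35 × 30% = 10.5; 25 × 30% = 7.5 and 35 × 60% = 21. On that model, a subject at 35 rather than 25 per week drops by 10 × 25% = 2.5 more episodes at a 25% response, and by 10 × 45% = 4.5 more at a 45% response.

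**3. Power on the protocol's scale.** This is a simulation of 20,000 trials per row, 20 v 20, mean baseline 30 per week. Reduction = baseline × percentage, with mean 25% on placebo and 25% + 5.0/30 = 41.7% on active. The percentage SDs are 4.5/30 = 15% and 7.5/30 = 25%. The CV rows are assumptions.

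| Baseline per week | Wilcoxon v rank ANCOVA, 0.05 | Gain (points) | Same, 0.0125 | Gain (points) |
|---|---|---|---|---|
| Uniform 25-35 | 76.8% v 77.3% | 0.5 | 53.8% v 55.4% | 1.6 |
| Lognormal, CV 0.3 | 66.9% v 72.3% | 5.4 | 42.4% v 50.2% | 7.8 |
| Lognormal, CV 0.5 | 55.2% v 66.8% | 11.6 | 30.9% v 44.1% | 13.2 |

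The within-arm rank correlation of reduction with baseline is about 0.15, 0.4 and 0.5 in the three rows. If the total SDs are instead held at 4.5 and 7.5, the comparison is 77.8% v 78.0% for 25-35, and 78.6% v 85.2% at CV 0.3.

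**4. Power with counts.** Here the endpoint is a 14-day Poisson count (25-35 per week is 50-70 per 14 days). Mean reductions are 45% v 25%, with a lognormal spread in individual response, one-sided 0.05. The ranges run from high to low assumed noise.

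| 14-day baseline | Wilcoxon | Rank ANCOVA | Gain at the two ends (points) |
|---|---|---|---|
| Uniform 50-70 | 48-75% | 52-83% | 4 and 8 |
| CV 0.3 | 43-66% | 49-78% | 6 and 12 |
| CV 0.5 | 40-59% | 48-76% | 8 and 17 |

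Gains are larger here because chance variation in the baseline count also enters the difference, and adjustment removes part of it. Across the means and noise levels tried, the gain at CV 0.5 is about 6 to 18 points.

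**5. Type I error.** With the same mean percentage reduction (25%) in both arms, rejection at nominal 5% under the model of step 3 was 5.0% (Wilcoxon) v 5.2% (rank ANCOVA) at 25-35 per week, 4.3% v 4.4% at CV 0.3, and 3.3% v 3.3% at CV 0.5. Neither test is inflated.

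**The case against.** The plan is coherent. The endpoint is the change in the number of episodes, the hypothesis concerns that reduction, and power is computed in episodes. Randomization makes the test valid, and chance imbalance in baseline is already part of its reference distribution. All of this stands.

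A material loss also needs a spread that the documents do not give. Eligibility does not settle it. Protocol 4.2.1 words Inclusion Criterion 8 as 3 or more episodes on each of 7 days (about 21 per week), while 4.1.4 and 4.1.5.1 describe 3 or more days per 7 with episodes (about 3 per week). With a floor of 42 per 14 days and mean 60 (resulting CV about 0.24-0.32, assumed), the count model gives 80% v 84% and 77% v 83% at low noise, and 49% v 52% and 47% v 51% at high noise. That is a gain of 3 to 6 points: smaller, but still a gain.

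Three further limits stand:

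- The gain presumes a roughly proportional effect or noisy baseline counts. If every subject lost the same number of episodes whatever the baseline, adjustment would gain nothing and could cost a little.
- Protocol 4.1.5.1 requires only "completion of the daily diary on at least 5 out of each 7 days during the last 14 days of the Baseline Symptom Assessment". Up to 2 × (7 − 5) = 4 of the 14 baseline days may be missing, and SAP 16.2.1.5 gives no proration rule.
- Protocol 2.5 already reports Week 12 interim results with the primary endpoint met at all doses, and SAP 4.2 treats that look as final for Week 12. Replacing a controlled test after seeing its data would be worse than the inefficiency.

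A reader might infer that the test is biased, that the percentages contradict the episode-based analysis, or that the 80% power is wrong. Steps 1 and 5 rule out the last and the first. As to the second, the protocol itself converts its percentages to episodes before computing power.

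**Conclusion.** The point holds as one of efficiency. The one controlled secondary test is valid but leaves collected baseline information unused, and under the protocol's own proportional expectation this costs power. The loss is from about 1 point or less to about 8 points within 25-35 per week, depending on the noise assumed. It is about 5 to 12 points at CV 0.3 and about 6 to 18 at CV 0.5. Both CVs are assumptions. A reader might take the largest figures as the trial's expected loss; the documents do not support that, since they state no baseline spread beyond the range for most subjects. Adjusting lost no power in any of the proportional-effect settings reported here.

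**What to change.** - In SAP 16.2.3.4 and protocol 8.8.3, specify a one-sided rank analysis of covariance (Quade) of the change in 14-day episodes. Use the baseline 14-day count as covariate and the same Holm step over doses.
- Make it the inferential test, with the unadjusted Wilcoxon supportive, only if this is fixed before the dysphagia data are unblinded. Otherwise keep the planned Wilcoxon and add the adjusted test as a labelled sensitivity analysis.
- State the expected SD of the baseline count on the 14-day scale (the present power inputs are per week), and one rule for missing diary days that applies at baseline and follow-up.
- Reconcile the two versions of Inclusion Criterion 8, which imply very different baseline minimums.

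The cost is SAP and protocol wording and a few lines of code, with no new data. After unblinding, the adjusted result carries supportive weight only.

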#### 8.8.3 Secondary and Exploratory Efficacy Analysis

Statistical tests to compare each APT-1011 dosing group with placebo will be performed for the secondary efficacy endpoints, but the corresponding p-values will be considered as descriptive rather than inferential. The secondary endpoints will be analyzed via a Cochran-Mantel-Haenzel test for categorical endpoints and analysis of covariance for change from baseline endpoints, except for the endpoint of time to relapse after initiation of double-blind treatment in Part 2, which will be analyzed using Kaplan-Meier methods.

As a secondary efficacy analysis, all 4 doses of active treatment will be pooled and compared to placebo with a one-sided test of two proportions.

Additionally,

a logistic regression model using both dose and frequency and dose-frequency interaction will be used to analyze the primary endpoint. Formal statistical hypothesis testing will be used to

Adare Pharmaceuticals SP-1011-002 APT-1011

evaluate treatment benefit with respect to the reduction in number of dysphagia episodes. For each dose that meets the criterion for statistical significance on the primary efficacy outcome, a Wilcoxon Rank-Sum test will be used to test whether the reduction in the number of dysphagia episodes from baseline is larger for the treatment group compared to the control. The hypothesis to be tested is:

 $H_0: R_{1i}(x) \leq R_{0i}(x)$ 

 $H_1: R_{1j}(x) > R_{0j}(x)$ 

Where  $R_{ij}(x)$  is the distribution function for the reduction in number of dysphagia episodes for treatment group i (=0 for control, 1 for treatment) and dose j. Holm's step-down procedure will be used to control the overall Type I error at 0.05, where the number of doses considered for inferential testing is equal to the number of doses that meet statistical significance for the primary efficacy analysis.

Statistical tests to compare each APT-1011 dosing group with placebo will be performed for other secondary efficacy endpoints, but the corresponding p-values will be considered as descriptive rather than inferential. The secondary endpoints will be analyzed via a stratified Cochran-Mantel-Haenzel test for categorical endpoints and analysis of covariance or Wilcoxon Rank-Sum tests for change from baseline endpoints, except for the endpoint of time to relapse after initiation of double-blind treatment in Part 2, which will be analyzed using Kaplan-Meier methods.

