- Section 8.2 There will be an additional analysis population called Full Analysis Set (FAS). FAS will be the primary analysis population for efficacy. ITT will also be shown but not considerd the primary effiacy

Author:

Version Number: 3.0

Version Date: 06NOV2019

Template No.: CS_TP_BS016 Revision 5 Reference: CS_WI_BS005

Page 15 of 70

population.

 Section 8.8.1 The gated analysis will be tested in the order of 3mg BID, 1.5mg BID, 3mg HS, 1.5mg HS and not follow what is in the protocol.

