16.1.3. PRIMARY ANALYSIS OF PRIMARY EFFICACY VARIABLE

The primary analysis of the primary efficacy variable (histological responder or non-responder) will be performed with a stratified CMH test using the two randomization strata: history of or current presence of esophageal stricture (yes/no) and prior positive steroid response to any corticosteroid treatment previously received to treat EoE (yes/no). There are 4 hypotheses corresponding to the 4 APT-1011 dosing groups, which will be tested using a gatekeeping strategy to preserve Type I error for each analysis.

Let θ j be the CMH common odds ratio comparing treatment vs. control for histologic response for dose j given the randomization strata; with j=1,2,3,4 corresponding to APT-1011 3 mg BID, 1.5 mg BID, 3 mg HS, 1.5 mg HS doses, respectively.

• Primary hypothesis #1

 $H_0: \theta_1 \le 1$ $H_1: \theta_1 > 1$

If the corresponding one-sided p-value from the CMH test of primary hypothesis #1, i.e., APT-1011 3 mg BID vs. placebo, is \leq 0.05, the null hypothesis will be rejected, and subsequently the following hypothesis will be tested:

• Primary hypothesis #2

 $H_0: \theta_2 \le 1$ $H_1: \theta_2 > 1$

Author:

Version Number: 3.0

Version Date: 06NOV2019

Template No.: CS_TP_BS016 Revision 5 Reference: CS_WI_BS005

Effective Date: 01Apr2018

Page 34 of 70

If the corresponding one-sided p-value from the CMH test of primary hypothesis #2, i.e., APT-1011 1.5 mg BID vs. placebo, is \leq 0.05, the null hypothesis will be rejected, and subsequently the following hypothesis will be tested:

• Primary hypothesis #3

H₀: $\theta_3 \le 1$ H₁: $\theta_3 > 1$

If the corresponding one-sided p-value from the CMH test of primary hypothesis #3, i.e., APT-1011 3 mg HS vs. placebo, is \leq 0.05, the null hypothesis will be rejected, and subsequently the following hypothesis will be tested:

• Primary hypothesis #4

 $H_0: \theta_4 \le 1$ $H_1: \theta_4 > 1$

If the corresponding one-sided p-value from the CMH test of primary hypothesis #4, i.e., APT-1011 1.5 mg HS vs. placebo, is \leq 0.05, the null hypothesis will be rejected.

Note the gate-keeping strategy only allows formal hypothesis testing of each dose if the higher doses all meet statistical significance. Given prior *studies* with histologic endpoints, there is a strong rationale suggesting that higher doses will have a greater benefit on the primary efficacy endpoint of histological response.

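### The histology sequence and the dysphagia Holm family each spend a full one-sided 0.05, so the stated overall 0.05 does not cover the two together

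*SAP*

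**What the plan says.** **Histology.** SAP 16.1.3 compares each dose with placebo on histologic response by stratified CMH tests. SAP 3.3 fixes the order: "The gated analysis will be tested in the order of 3mg BID, 1.5mg BID, 3mg HS, 1.5mg HS". When a one-sided p-value is at most 0.05, "the null hypothesis will be rejected, and subsequently the following hypothesis will be tested", again at the full 0.05. The section introduces the four hypotheses as ones "which will be tested using a gatekeeping strategy to preserve Type I error for each analysis".

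**Dysphagia.** SAP 16.2.3.4 applies a Wilcoxon rank-sum test against placebo "for each dose that meets the criterion for statistical significance on the primary efficacy outcome". Holm's procedure "will be used to control the overall Type I error at 0.05, where the number of doses considered for inferential testing" is the number d of doses that passed on histology. Since d may be anything from 1 to 4, the smallest p-value is compared with 0.05/d. Protocol 8.8.3 has the same rule: "Holm's step-down procedure will be used to control the overall Type I error at 0.05".

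**Scope.** SAP 6.6 sets the default: "The default significant level will be 5%; confidence intervals will be 90% and all tests will be one-sided". SAP 7.4 lists two controlled procedures. The first reads "The primary analysis of the primary efficacy variable will be performed using a gatekeeping strategy to preserve Type I error"; the second is Holm for dysphagia episodes. All other testing is called descriptive. Protocol 8.8.3 treats the dysphagia comparison as formal. No section divides alpha between the two families or makes dysphagia depend on completing the histology sequence.

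**The concern.** In a fixed sequence, the alpha released by a rejection moves to the next hypothesis. If the sequence stops at a failure, that unrejected hypothesis still holds the 0.05 and nothing remains to pass on. Here a second 0.05 opens the dysphagia family for whichever doses have passed, so the same alpha is used twice.

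A reader who sees two formal efficacy families, everything else labelled descriptive, and a claim of control over the *overall* Type I error may take 0.05 as covering both. In some configurations the chance of at least one false formal claim is nearly double that.

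**Working it through.** **Inputs from the documents.** One-sided 0.05 in each family (SAP 6.6, 16.1.3, 16.2.3.4); 20 subjects per arm with one shared placebo (protocol 8.1); response rates of 60% for the three higher doses, 20% for 1.5 mg HS and 10% for placebo; power 97.5% per dose and about 0.93 for three doses (protocol 8.1.1).

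**Assumption.** The histology-dysphagia correlation is not given, so 0 to 0.8 is shown.

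**Reproducing the plan's power.** The pooled rate is 0.35.
- Null SE = √(2 × 0.35 × 0.65/20) = 0.1508.
- Alternative SE = √((0.6 × 0.4 + 0.1 × 0.9)/20) = 0.1285.
- z = (0.5 − 1.645 × 0.1508)/0.1285 = 1.96, so power = 0.975, as stated.
- 0.975³ = 0.927, matching 0.93.

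The corresponding mean shift of the test statistic is 1.645 + 1.960 = 3.605. It is used for each effective dose below.

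**Closed form.** Suppose the effective leading doses are certain to pass. A joint error either includes a false histology rejection (probability at most 0.05) or occurs without one. In the second case the set of doses tested on dysphagia is fixed and Holm holds at 0.05. The joint error is therefore at most 0.05 + 0.05 = 0.10. With one effective dose and independent endpoints it is 1 − 0.95 × 0.95 = 0.0975.

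**Simulation.** Normal test statistics for four doses against a shared placebo; 400,000 trials per case, Monte Carlo SE about 0.0005; fixed sequence at 0.05, then Holm at 0.05 over the d passing doses; no true dysphagia effect unless stated. Where three values are given, the correlation is 0 / 0.5 / 0.8.

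| Truth on histology | Error within dysphagia | Joint error |
|---|---|---|
| First dose works, rest null | 0.048 / 0.053 / 0.059 | 0.096 / 0.093 / 0.090 |
| First two work, rest null | 0.045 / 0.047 / 0.052 | 0.093 / 0.089 / 0.086 |
| First three work, fourth null | 0.042 / 0.045 / 0.047 | 0.090 / 0.087 / 0.083 |
| None works | 0.003 / 0.012 / 0.025 | 0.050 throughout |
| All four work (certain to pass) | 0.041 throughout | 0.041 throughout |
| First null, other three work | 0.002 / 0.008 / 0.014 | 0.050 throughout |
| Planning case: 1.5 mg HS 20% v 10% | 0.041 / 0.045 / 0.046 | 0.041 / 0.045 / 0.046 |
| First three work and also help dysphagia (assumed shift 2.5), fourth null on both | 0.002 / 0.012 / 0.024 | 0.050 throughout |

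The histology sequence alone has error 0.050 wherever a true null can be reached. With three effective doses at only 50% power and the fourth null, the joint error is 0.057 to 0.074, so high histology power makes the inflation larger.

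The 0.059 within dysphagia arises because d is chosen from the same patients. A null dose that passes histology by chance tends, under positive correlation, to look favourable on dysphagia too.

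**Opening dysphagia only after all four histology rejections.** Joint error returns to 0.050 with one or three effective doses. The price, under the planning rates: the shift for 20% v 10% is 0.10/√(2 × 0.15 × 0.85/20) = 0.886, so power for that dose is P(Z > 1.645 − 0.886) = 0.224. All four pass in about 22% of simulated trials.

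**The case against.** **The word.** *Overall* can fairly be read as across doses within dysphagia: the sentence goes on to count doses, SAP 16.1.3 speaks of error for each analysis, and SAP 7.4 lists the procedures separately. A reader might infer that the plan breaks a promise of joint control. No section makes that promise, so this reading is not supported. What stands is that the scope is unstated, and that even the narrow reading is met only approximately (up to about 0.06).

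**The planning case.** A reader might infer that the design assumptions produce an error near 0.09. They do not: 1.5 mg HS is planned at 20% against 10%, so no histology null is true. Protocol 8.1.1 does warn that the lowest dose may be less effective, but inflation requires a dose with no effect at all.

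**Dysphagia effect.** Protocol 8.1.1 expects a larger reduction on drug than on placebo, though it admits a lack of earlier data. If the passing doses do help dysphagia, the joint error is about 0.05.

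**Status of the test.** SAP 16.2.3 opens by calling secondary p-values descriptive, and joint control in a Phase 2b study is partly a matter of preference. But SAP 7.4 and protocol 8.8.3 single dysphagia out as controlled and formal, so the claim made for it should be exact.

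**Practical effect.** Protocol 2.5 reports that histology was met at all doses. An all-four gate would then be satisfied and would change no dysphagia decision. This limits the consequence; it does not make the wording correct.

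**Conclusion.** The point holds as a fault in the stated error property. Joint one-sided family-wise error is about 0.083 to 0.096 at 97.5% histology power per effective dose (limit 0.0975, bound 0.10 when effective doses are certain to pass). It requires three things together: leading dose(s) effective on histology, a later dose null, and no dysphagia effect in the passing doses. It rests on a normal approximation and an assumed correlation of 0 to 0.8.

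It is about 0.05 or less if no dose works, all four work, the first dose is null, or the passing doses improve dysphagia, and in the planning case. The primary histology analysis keeps its 0.05.

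These figures count one dysphagia variable at one time. SAP 16.2.1.5 lists Weeks 12, 26 and 52, and SAP 16.2.3.4 puts dysphagia-free days in the same test sentence. If those were formal as well, more chances of a false claim would be added; that has not been quantified.

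**What to change.** In SAP 16.2.3.4, protocol 8.8.3 and the matching synopsis text, replace the claim about overall error, and add the same statement to SAP 7.4:

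- Holm controls one-sided error at approximately 0.05 across doses within the dysphagia-episode comparison only (simulated up to about 0.06 when few doses pass and the endpoints are strongly correlated).
- Histology and dysphagia are not jointly controlled; the one-sided family-wise rate over both can approach 0.10.
- The statement applies to one named time point and one named variable; other weeks and dysphagia-free days are descriptive.
- Dysphagia is reported as supportive of histology.

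The cost is a few sentences and a slightly less favourable stated property. No primary test changes.

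Opening the dysphagia family only after all four histology rejections would restore joint 0.05, but it is optional. Under the planning rates it would open in only about 22% of trials. Because protocol 2.5 already reports the Week 12 histology result, it would have to be declared as added after that result was known.
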